**Title: Testing a Brief Substance Misuse Preventative Intervention for Parents/Guardians of
5th-7th Grade Students**

NCT Number: NCT03925220

Study Protocol

Document Date: August 10, 2023; Revised: November 11, 2018

1.0 Purpose of the study:

The purpose of this study is to test the efficacy of a brief, communication-based, substance use preventive intervention for parents of pre/early adolescents. A parallel-group randomized controlled trial (RCT) to test the primary hypotheses that, relative to parents in the comparison condition, parents receiving the intervention, over the study period, will have, on average: 1) greater quality of interactions at meals, 2) a greater number of conversations about substances, and 3) higher quality of content in their conversations with their children about substance use. A companion primary hypothesis will be tested to determine if children of parents randomized to the intervention have fewer intentions and reduced willingness to use substances, reduced affiliation with substance-using peers, and increased negative attitudes and expectancies about substance use in contrast to children of parents in the comparison condition at study follow-up. We will also test a secondary aim's hypothesis, that children of parents assigned to the intervention condition will have a delayed initiation of substance use compared to the comparison condition.

2.0 Background / Literature Review / Rationale for the study:

Universal, family-based substance use preventive interventions have been shown to be efficacious, but programs that have been most effective are resource intensive and require extensive time and effort for program staff and participants. Therefore, an approach to universal substance misuse prevention is needed that is effective, resource-efficient, able to be disseminated easily, and sustainable.

3.0 Participant Population:

PHASE 1:

We propose to enroll parents of pre/early-adolescents (grades 5-7) with their child who live and attend school in Massachusetts.

Inclusion criteria include: 1) the parent must have a child between 5th-7th grades at the start of the project; 2) the parent must be the custodial parent, living with the child at least 50% of the time (as in the case of joint custody); and 3) parental consent and child assent are obtained. If a parent has more than one child that meets these criteria, the target child to participate in the intervention will be randomly chosen by research staff.

Exclusion criteria include: (1) the child has self-identified developmental disabilities who would have difficulty understanding the baseline assessment, and 2) the parent or child does not adequately speak, read, and comprehend English or Spanish well enough to complete study procedures.

PHASE 2:

Inclusion criteria: child and parent participants that consented/assented to participate in Phase 1 and were randomized.

Exclusion criteria: 1) parent participant does not consent to being followed up for other studies

4.0 Special Populations:

PHASE 1 & 2:

- Children
- Fetuses/Neonates
- Prisoners
- Members of the military
- Non-English speakers
- Those unable to read (illiterate)
- Employees of the researcher
- Students of the researcher
- Adults lacking capacity to consent and/or adults with diminished capacity to consent, including, but not limited to, those with acute medical conditions, psychiatric disorders, neurologic disorders, developmental disorders, and behavioral disorders
- Disadvantaged in the distribution of social goods and services such as income, housing, or healthcare
- Fear of negative consequences for not participating in the research (e.g. institutionalization, deportation, disclosure of stigmatizing behavior)
- Approached for participation in research during a stressful situation such as emergency room setting, childbirth (labor), etc.

5.0 Research Locations and Sample Size:

5.1 Research Locations

PHASE 1:

We will be working with schools in Massachusetts. We will obtain approval from schools prior to beginning any data collection. Once school district approval is received, data collection will begin and we will submit these letters of approval to the IRB to maintain an up-to-date list of school districts. Tufts University School of Medicine and Participant Homes will also serve as locations for data collection and intervention sessions.

PHASE 2:

All study activities will be done virtually/online.

5.2 Sample Size

PHASE 1:

The number of participants from each school will depend upon the number willing and available to participate in each school district, and the total number of participants from all sites combined shall not exceed 1500 (750 parent/child dyads). Note: Sometimes

participants are referred to as parent/child dyads in participant facing materials, but all verbal communication clarifies that a parent/child dyad or pair consists of 2 participants.

PHASE 2:

We will not recruit any new participants for this portion of the study.

Procedures Involved:

PHASE 1:

Eligible, consenting parents and their assenting child will complete baseline assessments related to their family practice of eating meals together, communication skills, parenting styles, and their own substance use. Parents will then be randomly assigned to one of two conditions: 1) intervention, or 2) comparison. Parents and children will then be followed at four follow-up points at 3, 6, 12, and 18 months.

Brief Preventive Intervention Condition. While the intervention will only be given to the parent participants, the parent and their child will be administered survey-and video-based baseline and follow-up assessments. After parent participants complete the baseline assessments, they will be given a handbook specific to the gender of their child, written on an eighth-grade reading level that provides information and advice on six domains: 1) background on adolescent SU, including up-to-date statistics on the prevalence of use of different substances by youth and effects of SU on the developing brain; 2) parent-child communication, including the importance of open communication, monitoring, and ways to communicate effectively; 3) eating at least five meals per week with their children, including information on which meals parents should eat with their children, what to avoid doing during meals (for example, watching television, or using phones to talk, text, or search the internet), and alternatives if eating meals together is not possible; 4) parent-child communication specifically about the harms of SU, including understanding why teenagers use substances, finding out what their children already know, providing facts about substances, ways to explain why their children should not use substances, setting clear parental expectations, setting a good example, addressing problems with permissive parenting around SU, and sample conversation starters; 5) the role of substance-using peers with respect to adolescent substance use and effective peer management strategies and 6) additional resources, which are available through a study website with links to resources for additional information (to be printed out for parents without internet access). The handbook will be available on a portable USB flash drive and on the study website. The primary differences in the content of the handbooks by gender are in: 1) the statistics about SU, 2) the section on reasons why teens choose to use substances, which are different for adolescent boys and girls, 3) ways to help boys and girls meet distinct needs without substances; and 4) gender-specific resources available to parents.

The intervention will comprise of two components: in-person or via video conference, and home-based. Parents will be instructed to read the handbook in its entirety before the in-person/video conference session. One-to-two weeks after receiving the handbook, parents will participate in a one-hour session with an interventionist where the main points in the handbook will be reviewed. Parents will also be given the opportunity to ask questions to increase their competencies around the handbook

suggestions. Additionally, with guidance from the interventionist, parents will fill out an action plan on how to make changes in family meals and communication about substances with their child. The interventionist will also provide parents with a referral packet, which will include resources for child and adult mental and physical health services, substance-related services, and will have insurance required, as well as free provider options. In response to parent feedback from the uncontrolled pilot indicating a desire to have more contact with the study interventionist, which we tested in the pilot RCT, two weeks after the in-person session, participants will have a half-hour follow-up phone call with the same study interventionist to go over the action plan and answer any questions that have arisen after parents have had an opportunity to implement changes with their children. Communication specialists will conduct the in-person/video conference sessions. For the home-based component, parents will receive two messages each week with reminders and tips that reinforce the information covered in the handbook. Parent participants who do not have their own cell phone will be provided a disposable phone, which will allow access to text messages. Parents who do not know how to text will be given a tutorial during the intervention session. Finally, participants will receive a magnet about the importance of family meals that they will be instructed to put on their refrigerators. Parents and their target child will complete post-intervention 3-, 6-, 12-and 18-month follow-up survey assessments and 3-, 6- and 12-month follow-up video and audio assessments. Weight and height measurements will be taken during baseline for child participants. To minimize the threat of group cross-contamination due to randomization at the individual, rather than school level (see Design Considerations), participants in the intervention condition will be apprised of the importance of not sharing any information about the intervention with other parents during the intervention period. They will be informed that after study completion, all parents in the school will be offered intervention materials. The level of cross-contamination will be assessed by asking parents at the end of the trial if they shared information with or received information from other parents, and through a cross-contamination measure (see Measures).

Comparison Condition. Parents and children in the comparison condition will be administered the baseline survey, video assessments and child weight/height measurement, and the follow-up survey (3, 6, 12, 18M) and video/audio (3, 6, 12, and 18M) assessments on the same schedule as intervention participants. For the comparison condition, after the baseline assessment, parents will receive a handbook on the importance of nutrition and physical activity for children entitled: "Healthy Eating & Physical Activity Across Your Lifespan: Helping your Child –Tips for Parents" with an insert on weight talk that was developed by the research team. The handbook, which is sponsored by the National Institute of Diabetes and Digestive and Kidney Diseases and the Weight Control Information Network, is approximately the same length as the intervention handbook and is available in English and Spanish. They will also receive a magnet with a message about nutrition and exercise. To control for contact time, these participants will also meet in-person/video conference with a study staff member to go over the comparison handbook material and complete an action plan two weeks after receiving the handbook and complete an action plan, as well as have a half hour follow up phone call two weeks after the in-person/video-conference session. Parents will

receive two text messages twice per week for 13 weeks with tips and reminders from the comparison handbook.

Duration of participant involvement:

Week 0: Baseline survey, video family meal and audio conversation recordings, and child weight/height measurement

Weeks 1-13: Intervention (Intervention group activities include receiving handbook, in-person/video conference intervention, follow-up phone call, and text-messaging; control group activities include receiving handbook, in-person/video conference meeting, follow-up phone call, and text-messaging.)

Week 13: Post-intervention survey and audio conversation recordings

Week 26: 6-month survey and video family meal and audio conversation recordings

Week 52: 12-month survey and video family meal and audio conversation recordings

Week 78: 18-month survey and audio conversation recordings

Surveys and videos can be completed within +/- 2-week period of the given week.

Participants that do not complete the surveys or videos within the given time period will be followed up with and asked to provide missing data. If changes are made to survey instruments after participants have already received the instrument, study staff will treat this as missing data and will contact participants to obtain the missing data.

A set of questions related to participants' experiences during the COVID-19 pandemic (March 2020-April 2021) will be appended to the end of all currently enrolled participants' next timepoint survey [as of approval from IRB from this submission on 27 Sep 2021]. Both parent and child will be asked to complete questions (6 and 2 additional questions, respectively). Participants have the option to skip any questions they do not feel comfortable responding to. The questions will only be asked once.

In situations where participants express interest in continuing with the study but lack time to complete materials for a specific time point, participants will have the option to complete a shortened survey. They will specifically consent/assent to taking this shortened survey and receiving a \$5 (3- or 6-month) or \$10 (12- or 18-month) Amazon e-gift card. This consent/assent process is completed at the beginning of the shortened survey.

The expected duration of the study is 5 years.

When a participant completes the study, we will complete the following steps:

- Offer the other group's materials to be emailed or mailed to them
- Send them the completion email and request a response to confirm their acknowledgement of completion
- Send them instructions on what to do with the tablet
- Ask them to complete a form which asks for consent to keep their contact information if they have not already completed this form at a previous timepoint

(participants may complete this form at any point during the study) for potential future studies

We will keep all contact information of adult participants for future study purposes who consent to us keeping their information for this purpose. This contact information will be kept in its own Box folder, separate from any data or other study-related files. For those that do not consent to us keeping their contact information, we will delete their contact information after five years after the cessation of the study as per the protocol (Section 17.0 Data Management and Confidentiality).

PHASE 2:

Participants that are currently enrolled in the study will be contacted and asked to consent to the continued follow-up (i.e. Phase 2) to begin three months after they complete Phase 1's final follow-up point at 18-months (i.e. their first survey for Phase 2 will occur 3 months after Phase 1's 18-month follow-up time point).

Participants that have completed Phase 1 already, will be contacted and asked to consent to start the Phase 2 follow-up immediately.

All eligible, consenting children only will be asked to complete a brief online survey (approximately 5 minutes) every three months for up to two years. There are two different surveys (i.e. "Int" and "Cont") Only one will be administered at each time point and we will switch back and forth at each time point (e.g. first survey will be "int" then at next follow up the "Cont", then "Int", etc.). The "Int" survey will ask about the child's mental health, substance use initiation, willingness to use, intentions to use and peer use, as well as, the frequency of substance use conversations they have with their parent. The "Cont" survey will ask about the child's substance use initiation, the child's perception of body image/weight, child's mental health and other weight-related behavior questions.

PHASE 1:

Instrumentation

- Questionnaires
- Video: Video observation of family meals and parent-child discussions about substance use
- Audio: intervention in-person/video conferenced sessions will be recorded for quality assurance
- Other: height/weight measurement of children

Online Instrumentation

- The online survey engine REDCap will be used to present the surveys.
 - <https://collaborate.tuftsctsi.org/redcap//index.php?action=myprojects>
- Online recruitment agencies will have their own method of distributing the approved screening and eligibility survey to potential participants, such as a Qualtrics or REDCap survey.

- Participants will be able to complete the entire survey if they abstain from answering certain questions.
- Paper surveys are also available.

PHASE 2:

Online Instrumentation

- The online survey engine REDCap will be used to present the surveys. We will use the same database that Phase 1 documents are stored/administered from.
- Participants will be able to complete the entire survey if they abstain from answering certain questions.

5.2 Additional Safeguards for Special Populations:

PHASE 1 & 2:

Children

The inclusion of children is necessary as this is a prevention study to conduct research with children. The study is designed as a prevention program for kids and families.

It is possible that situations will arise in which interventionists or other study team members are provided with information by children or families, which they are legally and ethically obligated to disclose. This will be in accordance with the Massachusetts state statutes for making a report for children, as delineated in the following document: <https://www.childwelfare.gov/pubpdfs/manda.pdf>. According to the statute in the state, “a mandated reporter must report when, in his or her professional capacity, he or she has reasonable cause to believe that a child is suffering physical or emotional injury resulting from:

- Abuse inflicted upon the child that causes harm or substantial risk of harm to the child’s health or welfare, including sexual abuse;
- Neglect, including malnutrition;
- Being a sexually exploited child; and
- Being a human trafficking victim as defined by chapter 233, § 20M.”

Further assessment of parental drug use as child abuse will be assessed as well, in accordance with the following document:

<https://www.childwelfare.gov/pubpdfs/drugexposed.pdf>. Communication with the Tufts University IRB indicated that knowledge of substance use by youth is not necessarily indicative of abuse or neglect, and reporting in those situations without other cause to suspect abuse or neglect would be an unnecessary breach of confidentiality.

If any problems are reported or identified during any point of the study, appropriate referral for services or psychological intervention will be arranged. While the questionnaires do not touch on these topics, it is possible that situations will arise in which interventionists or other study staff members are provided with information by children or families which they are legally and ethically obligated to disclose (i.e.,

child abuse or neglect, whether or not in the context of parental substance use). All participants are informed in advance through the process of informed consent (or assent for child participants) of the legal and ethical obligations of study staff should these issues arise. Whenever possible, study staff will handle these situations therapeutically. For example, if time limits and safety concerns allow, parents will be informed in advance and provided the opportunity to participate in the mandated report process. Research staff will contact [name], the Co-PI (a clinical psychologist) who will be responsible for any on-site clinical decision-making.

Any adverse events that are observed and/or reported during assessments or intervention sessions will be reported immediately to [name]. All adverse events will be reported in writing to the IRB within one week. All serious adverse events will be reported to the Tufts IRB immediately by telephone and by written report within 24 hours of our receipt of information regarding the event. NIH will be informed of any serious adverse events and action taken as a result of the IRB's recommendations.

SAEs will be reported to the NIDA PO within 24 hours of the event by email. This notification will include a brief explanation of the SAE and when it occurred. A written follow up will be sent within 72 hours of the event and will include information on the date of the event, what occurred, actions taken by project staff, planned follow up (if any), the intervention group/study arm of the affected participant (if relevant), whether the event appears to be related to the intervention, and whether the event affects future participation.

Non-English speakers

The inclusion of Spanish speakers (who are non-English speakers) is necessary in order to ensure a sample that is as diverse and representative of the population as possible. All study materials are available in Spanish, and members of the study staff, including interventionists, are fluent in Spanish. Any participant who feels more comfortable speaking, reading, and writing exclusively in Spanish will be able to complete all study procedures entirely in Spanish and will be able to speak Spanish with study staff.

Copies of all Spanish translations will be submitted to the IRB along with the required "Certificate of Translation."

Those unable to read (illiterate)

The inclusion of those unable to read (illiterate) is necessary due to universal nature of the intervention. Given the universal nature of the intervention, we aim to ensure that it is accessible to all people in the areas we will be working. Some school districts in Massachusetts have a high level of parental illiteracy, and it is necessary to ensure that the study is equally accessible for all potential participants.

In order to ensure participants with low or no levels of literacy understand the study fully, study staff will carry out the full consent process for those unable to read (detailed in the consent section of the protocol).

6.0 Investigational Medical Devices:

N/A

7.0 Incomplete Disclosure or Deception:

N/A

8.0 Recruitment Methods:

PHASE 1:

Recruitment Techniques

- Email or web postings
- Letters to professionals/institutions
- Letters to parents/guardians
- Brochures, flyers, and/or pamphlets
- Letters to subjects (information sheet to children)
- Online recruitment
- Snowball recruitment, including but not limited to online recruitment platform
- Online informational events for parents hosted by ourselves or others which include recruitment information
- Other (explain): in person

To obtain a diverse sample of parents of 5th-7th grade students, participants will be recruited from schools in Massachusetts. Recruitment will take place in Years 1-3. Study staff members will recruit participants during the school year via in-person recruitment at the end of the school day and within afterschool programs, open houses, PTA meetings, and flyers put up at the school. School administration will have the ability to request their preferred type of recruitment material(s) to send out or distribute using their preferred methods, including, but not limited to: email blasts, school newsletters, social media, letters sent home to students, presentations, phone calls, automated phone calls, flyers, etc. These requests can include school-specific modifications, if the administration prefers. Whenever possible, we will screen on site. For those who cannot screen on site, study staff will collect contact information and organize a separate time to contact interested parents to be screened and then scheduled for an initial survey. In cases where there is limited time to collect contact information, interested parents will be given flyers instructing them to contact study staff at their convenience. Parent participants will be randomized to the intervention or comparison conditions, but child participants will only complete assessments. The PI, [name], will not participate in active recruiting procedures at Milton Public Schools due to her possible prior relationship with parents and their children to prevent undue coercion (see further

details in Section IX. Consent). Process).

In order to recruit outside the school setting, particularly given COVID-19, we are hiring an external recruitment agency to recruit dyads. We have received approval from NIH to use this method beginning June 1, 2020. The agency's role would entail recruiting eligible families from their lists of contacts, with a specific focus on recruiting a diverse sample. Once eligible and interested participants are identified, our team will receive their contact information. The study team will then contact them and follow all screening and eligibility procedures as currently outlined. This will be done to supplement the above school-based recruiting strategies. As described above (Section 6.0; Online Instrumentation), the agency will use its own platform to distribute the screening and eligibility survey.

In addition to the above-mentioned method of online recruitment, we also plan to utilize recruitment services that post the study opportunity on professional, pre-existing social platforms that are not affiliated with Tufts or any of the study personnel. For example, professional organizations that specialize in using social media to post and share study opportunities, but without collecting any personal/participant data (e.g. Craigslist, Call For Participants). Additionally, to reach more participants, we plan to do targeted advertising using Meta social platforms, including Facebook and Instagram. In order to do this, Meta requires an account. We will make SUPPER Project Facebook and Instagram accounts which only have the project name, brief description of the study, and link to the REDCap sign up form. We will use previously approved recruitment materials (e.g. flyers, information sheets, etc) as content. All interested persons will be asked to follow a link to the REDCap online screener that the study team manages where we will obtain their contact information to be able to contact them for next steps.

In order to increase recruitment numbers, we are using the online recruitment agency's built-in snowball recruitment method. All current participants recruited through the online platform and those recruited outside the outline platform, but willing to make an account, can send referrals to other families they believe would be interested in participating. For each successful recruitment (i.e. they consent to participating in our study), the recruitment agency provides a standard minimal incentive to the referring participant. We will also use traditional snowball recruitment method techniques to encourage participants to share the opportunity with those they believe may be interested.

Another recruitment strategy we are planning is to use is to host online, informational events for parents with the goal of providing parents important information as well as to disseminate recruitment information. An example of this would be: we partner with an organization specializing in a related health topic (e.g. adolescent mental health) where the partner agrees to provide information about their topic to families. Before and/or after their presentation we present the study as an opportunity to families using previously approved materials (i.e. Recruitment Video and/or Recruitment PowerPoint Presentation). To advertise for these events, we will use methods such as the ones listed above (e.g. sending flyers, snowball email, using school staff to disseminate opportunity, etc.), in addition to any strategy the partner wishes to use.

PHASE 2:

Participants will be recruited by contacting them up to four times within two weeks using one or more of the following methods:

- Postcard
- Email
- Phone call
- Text message

Additionally, all participants will receive information about participating in Phase 2 via the newsletter.

Participants who do not respond to the initial contact as outlined above may be contacted again in additional efforts to retain the most number of participants from Phase 1.

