**NCT Number: NCT03925220**

**Statistical Analysis Plan**

**Document Date: August 10, 2023; Revised: November 11, 2018**

## **Data Analysis Plan**

The scientific rigor of this application is reflected in our preliminary analyses, missing data detection and correction procedures, and our data analytic strategies. First, all forms will be checked for missing data and outliers prior to data entry. Attrition effects will be evaluated by testing whether systematic differences exist between participants who complete the research versus those who drop out. We will also examine any pre-existing differences between the two conditions in demographic composition and all measures collected at baseline. Pre-existing group differences in these variables will be accounted for in subsequent analyses, using baseline scores as covariates. Participants will be included in the analysis if they are randomized (i.e., intention -to-treat).

Participants who are lost to follow-up or drop out can affect the validity of the group comparisons if: 1) the outcome of interest is related to being lost or dropped, and 2) it is differential between groups. The missing data mechanism will be formally tested to determine whether it is Missing Completely at Random (MCAR) or Missing at Random (MAR). For completeness in assessing the effect of missingness, two additional analyses will be conducted: 1) a 'per-protocol' analysis among participants who complete all follow-up surveys; and 2) multiple imputation of five data sets using a discriminant function for binary outcomes and Markov chain Monte Carlo for continuous outcomes, assuming the missing data mechanism is MAR.

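### Changed baseline survey items are to be collected retrospectively with no closing date, so answers given after randomisation can enter the Aim 1 and Aim 2 survey-outcome models as baseline scores

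*Protocol*

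**What the plan says.** All protocol text here is in section 5.2, Procedures Involved, Phase 1, unless noted.

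- **Schedule.** Baseline is week 0 ("Week 0: Baseline survey, video family meal and audio conversation recordings"). The programme follows ("Weeks 1-13: Intervention"), with follow-ups at weeks 13, 26, 52 and 78. The window is stated as: "Surveys and videos can be completed within +/- 2-week period of the given week".
- **Missed assessments.** "Participants that do not complete the surveys or videos within the given time period will be followed up with and asked to provide missing data".
- **Changed instruments.** "If changes are made to survey instruments after participants have already received the instrument", then "study staff will treat this as missing data and will contact participants to obtain the missing data".
- **Order at entry.** Baseline assessments come first, then randomisation. Intervention parents receive the handbook after completing baseline.
- **COVID-19 items.** These were added to each enrolled participant's next survey and asked once.
- **Skipped items and paper forms.** Under Online Instrumentation, a participant may leave questions unanswered and still finish a survey. Paper surveys are also available.

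The SAP (Data Analysis Plan) adjusts the Aim 1 and Aim 2 models for baseline scores. It also compares the arms on all baseline measures, and says: "Pre-existing group differences in these variables will be accounted for in subsequent analyses, using baseline scores as covariates". Multiple imputation is one of two additional analyses, with methods named for binary and continuous outcomes. The SAP has no visit-window rule and no rule for answers collected late.

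**The concern.** The changed-instrument sentence is an instruction, not merely a gap. It applies to any survey instrument already received, and the baseline survey is one. A family that has had the handbook, the session and the text messages can be asked a changed baseline item, and the protocol treats the answer as missing data now supplied. Skipped baseline items open the same route if staff also pursue those, which the text does not settle.

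A covariate measured after treatment has begun can be affected by treatment. Adjusting for it removes whatever part of the effect it already carries. The SAP's baseline comparison adds to this: a difference that the intervention produced in such an item would be read as pre-existing and adjusted away.

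The outcomes exposed are those measured by survey: how often parents communicate about substances (Aim 1), and the children's intentions, willingness, attitudes, expectancies and peer affiliation (Aim 2).

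**Working it through.** The documents give no figure on this point to reproduce. The check has three parts.

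**1. Which baselines are exposed?**

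| Baseline data | Covered by the changed-instrument rule? | Protected by the order of entry? |
|---|---|---|
| Mealtime video and conversation recordings | No, the rule concerns survey instruments | Yes, largely |
| Baseline survey missed altogether | No, it falls under the missed-assessment rule | Yes, largely: randomisation and handbook follow baseline |
| Baseline survey item changed later | Yes | No |
| Baseline survey item skipped | Not clearly; depends on whether staff pursue it | No |

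Taken alone, the week-0 window runs from week -2 to week 2 and overlaps the first two weeks of the intervention period. Because the handbook follows completion of baseline, that overlap is not a separate fault.

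**2. What does a late baseline score do to the adjusted estimate?**

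Use a linear approximation. Let the outcome be Y = ρX + δT + error, where X is the true baseline score, T the arm and δ the effect. Suppose a share f of intervention-arm baseline scores is collected late and carries a fraction λ of the effect. The recorded baseline means then differ between arms by fλδ, and the adjusted estimate is

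δ − ρ·fλδ = δ(1 − ρfλ).

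Changes over time common to both arms cancel if back-filling is equally frequent in both. None of ρ, f and λ is in the documents. The ranges assumed are ρ 0.3 to 0.7, f 5% to 30% and λ 0.5 to 1. Share of the effect kept with λ = 1:

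| ρ | f = 5% | f = 10% | f = 20% | f = 30% |
|---|---|---|---|---|
| 0.3 | 0.985 | 0.97 | 0.94 | 0.91 |
| 0.5 | 0.975 | 0.95 | 0.90 | 0.85 |
| 0.7 | 0.965 | 0.93 | 0.86 | 0.79 |

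- Least kept: 1 − 0.7 × 0.30 × 1 = 0.79.
- Most kept: 1 − 0.3 × 0.05 × 0.5 = 0.9925, or about 99%.

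A simulation with 400,000 records, δ = 0.25 SD and λ = 1 gave 0.970, 0.928 and 0.934 at f = 10%, and 0.908, 0.861 and 0.784 at f = 30% (ρ = 0.3, 0.5, 0.7 in turn). The largest departure from the formula is 0.022, at ρ = 0.5 and f = 10%. Simulation error there is about 2 × 0.866 / √400,000 / 0.25 = 0.011 per value, so the departure is about two standard errors. The simulation confirms the algebra and says nothing about the inputs.

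**3. What of late follow-up answers?**

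The windows are weeks 11–15, 24–28, 50–54 and 76–80. A 3-month answer given after week 19.5, the midpoint of 13 and 26, is nearer the 6-month point; the later midpoints are weeks 39 and 65. The protocol sets no limit on late collection and does not say which time point a late answer belongs to. This shows that the label matters, not that answers are mislabelled.

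**The case against.** **Most baselines are safe.** This stands. The order of entry protects recorded baselines and wholly missed baselines, so mealtime quality and conversation quality, the two Aim 1 outcomes analysed by linear mixed model, are largely untouched.

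**The arithmetic models a different kind of outcome.** This stands too. The exposed outcomes are proportions analysed by log-binomial GEE, so the linear percentages do not carry over directly. A reader might infer that the effect could be halved, since 1 − 0.5 × 1 × 1 = 0.5. That needs every baseline score to be late with the whole effect already in each. The documents do not support it: families enrolled after a change would receive the changed instrument at entry, a changed item is only part of a multi-item score, and no document says that a primary-outcome item was ever changed.

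**Wrong labelling of follow-ups is inferred from silence.** A reader might conclude that late answers are filed under the earlier follow-up, blurring the condition-by-time test and dating first substance use too early in the initiation model. The protocol states no filing rule, so this is a possibility that nothing prevents rather than something the plan does.

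**Pursuing late responders limits attrition.** This is fair. The SAP names loss to follow-up as a threat to validity. A hard cut-off for follow-up answers would exchange timing error for missing data, and the documents do not show which is worse.

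None of this answers the narrow point: the rule reaches baseline survey items, and the SAP uses baseline scores as covariates.

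**Conclusion.** The concern holds for baseline survey items that are changed after receipt, and for skipped items if staff pursue them. Followed as written, the protocol allows answers given after randomisation to act as baseline covariates in the Aim 1 communication-frequency model and the Aim 2 models. The bias is toward no effect, provided that baseline and outcome are positively related and the late answer already reflects some of the intervention's effect.

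The size cannot be known from the documents. On the assumed ranges about 79% to 99% of the effect is kept, as a rough guide only. If few items were changed, the loss is small. The documents do not support a claim that follow-up answers are misfiled, or that the recorded outcomes are affected.

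**What to change.** 1. **Baseline rule.** State in the protocol's changed-instrument sentence and in the SAP that a survey answer obtained after randomisation is never used as a baseline score.
2. **Changed items.** Add them prospectively at the participant's next time point, as was done for the COVID-19 items.
3. **Dates.** Record the actual completion date of every survey, paper forms included. The documents name REDCap but do not mention time stamps, so availability for data already collected should be confirmed.
4. **Missing baseline in the primary models.** Multiple imputation is only an additional analysis and its methods are given for outcomes. The SAP should therefore say how a missing baseline score enters the primary models, for example by simple imputation of the covariate ignoring arm. Otherwise a blanked baseline would by default drop a randomised family, against the SAP's intention-to-treat statement.
5. **Follow-up answers.** Keep collecting late responses. Add a sensitivity analysis that excludes out-of-window answers or re-classifies them by completion date, excluding them where the later time point already has its own answer.

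The cost is a few sentences in each document and a little more data cleaning. Some baseline answers now counted as complete would become missing.
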